6.3 Laboratory Data

Clinical laboratory evaluations include:

- Hematology: hemoglobin, hematocrit, red blood cell count, white blood cell count with differential, and platelets
- Serum Chemistry: sodium, potassium, chloride, bicarbonate, calcium, glucose, BUN (urea), serum creatinine, uric acid, ALT, AST, alkaline phosphatase, LDH, total protein, albumin, total bilirubin, direct bilirubin, indirect bilirubin, CPK (with fractionation, if available)
- Lipid Panel: Cholesterol, LDL, HDL, triglycerides (screening only)
- Estimated glomerular filtration rate (eGFR) using the estimated MDRD formula will be calculated and reported by the central lab at each visit that the clinical laboratory test is collected.
- Urinalysis: pH, specific gravity, protein, ketones, nitrites, urobilinogen, leukocyte esterase, protein, glucose, microalbuminuria, and blood. If blood, protein, or leukocytes are positive, reflex to microscopic examination.
- Urine drug screen: for drugs of abuse

Clinical laboratory values will be expressed using both Standard US units and SI units. Tabulations, listings, and graphics will be provided to show the data in both systems. The observed value and change from baseline will be summarized for select continuous laboratory parameters. In addition, shift tables (low, normal, high) will be presented. For AST and ALT, the shift tables will use the categories: Normal, >ULN, >3x ULN, and >5x ULN. In the event of repeat values from the same visit, the non-missing value closest to the target date for the visit will be used. In the case of a tie, the latest record will be used.

All laboratory data will be provided in data listings. Additional listings will be presented for all abnormal laboratory values.

On-study laboratory abnormalities are those with an assessment date after the date/time of first dose of study drug and within 30 days after the last dose of study drug.

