1.3.4 Clinical Adverse Event Profile

To date, 7 clinical studies have been completed in healthy volunteers and migraineurs that inform PK, metabolic interactions, safety, tolerability and efficacy. In total, the current data suggests a favorable benefit-risk profile for rimegepant in the acute treatment of migraine attacks. Efficacy was established in Study CN170003, and the overall database suggests a favorable safety profile. Clinical experience with rimegepant has also allowed the characterization of safety and tolerability at substantial multiples of the intended therapeutic exposure and intended frequency of use. Rimegepant has been assessed in single doses up to 1500 mg and in multiple doses from 75 mg to 600 mg with 14-days of dosing (including 300 mg twice daily), where the higher doses yielded exposures more than 60 times greater in AUC and 30 times higher in C_{max} as compared to the mean therapeutic exposure of a single 75 mg dose. These high exposure multiples were generally well tolerated and safe.

CCI

CCI

Rimegepant appears to be generally safe and well tolerated in humans when given as single oral doses up to the maximum dose of 1500 mg and multiple oral doses up to the maximum daily dose of 600 mg for 14 days. Please refer to the Investigators Brochure for a summary of the clinical safety profile.

The primary identified AE of interest is potential change in liver functions tests. Investigators must carefully monitor routine liver functions tests (ALT, AST, total bilirubin, and ALP) and potentially liver related symptoms and signs. Clinicians should also monitor changes in hematology and other laboratory measures. Please refer to the current Investigators Brochure for further information regarding the clinical safety profile of rimegepant.

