4.3.4 End of Treatment (7 days after Treatment)

Patients will return to the study site within 7 days of study treatment (+2 days) for review of the eDiary assessment of medication compliance, and monitoring of tolerability and safety (including vital signs, laboratory tests, and electrocardiography). If a patient has NOT experienced a migraine headache of sufficient severity within 45 days after randomization, he or she will be withdrawn from the trial and instructed to return unused study medication and eDiary to the study center.

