8.1.5 Potential Drug Induced Liver Injury (DILI)

Wherever possible, timely confirmation of the initial liver-related laboratory abnormalities should occur prior to the reporting of a potential DILI event. All occurrences of potential DILIs, meeting the defined criteria, must be reported as SAEs as per Section 8.1.2.

Potential drug induced liver injury is defined as:

1. Aminotransferases (AT) (ALT or AST) elevation > 3 times the upper limit of normal (ULN)

AND

2. Total bilirubin (TBL) > 2 times ULN, without initial findings of cholestasis (elevated serum alkaline phosphatase)

AND

3. No other immediately apparent possible causes of AT elevation and hyperbilirubinemia, including but not limited to, viral hepatitis, pre-existing chronic or acute liver disease, or the administration of other drug(s) known to be hepatotoxic.

If any potential DILI is identified and meets the criteria above, the Biohaven Medical Monitor (or designee) should immediately be contacted for further instruction on dosing adjustments and whether the patient must discontinue from the trial and appropriate follow up requirements.

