5.2.9 Visit Windows

Windows for the timeframe around efficacy measurements (15, 30, 45, 60, 90 minutes, 2, 3, 4, 6, 8, 24, and 48 hours) will be automated and captured in the eDiary. Refer to Table 6 for details on the evaluation intervals and Appendix 1 for details on the schedule of assessments.

Evaluation Protocol-Specified Interval		Analysis-Specified Interval		
Screening Phase				
Screening	Day -28 to Day -3	Day -40 to Day -3		
Acute (Randomization) Phase				
Baseline (Randomization)	Day 1	Day -2 to 1		
Onset of Migraine	Day 1 to 45	Day 1 to 45		
15, 30, 45, 60, 90 minutes post- dose	Time of Dose + 15, 30, 45, 60, and 90 minutes	Time of Dose + 15, 30, 45, 60, and 90 minutes (as captured in eDiary)		
2 hours post-dose	Time of Dose + 2 hours	Time of Dose + 2 hours (as captured in eDiary)		
8 hours post-dose	Time of Dose + 8 hours	Time of Dose + 8 hours (as captured in eDiary)		
24 hours post-dose	Time of Dose + 24 hours	Time of Dose + 24 hours (as captured in eDiary)		
48 hours post-dose	Time of Dose + 48 hours	Time of Dose + 48 hours (as captured in eDiary)		
End of Treatment Visit	Time of Dose + 7 days	Time of Dose $+ 2$ to 21 days		

Table 6: Evaluation Intervals for Efficacy Analysis

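### The repeat-value rule in SAP 6.3 can let a retest displace an early abnormal laboratory result from the shift tables, leaving a gap for non-hepatic tests and mild AST/ALT elevations

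*SAP*

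**What the plan says.** SAP 6.3 (Laboratory Data) plans two kinds of summary. The first is continuous: "The observed value and change from baseline will be summarized for select continuous laboratory parameters". The second is shift tables, in low/normal/high categories, with multiples of ULN for AST and ALT. The same paragraph then says how to choose among repeats: "In the event of repeat values from the same visit, the non-missing value closest to the target date for the visit will be used". It adds: "In the case of a tie, the latest record will be used". Neither sentence looks at whether the value is abnormal.

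The protocol's Schedule of Assessments (Table 1) has safety laboratory tests at Screening and at End of Treatment only, so a subject's post-dose shift category normally rests on one selected value.

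The only target and window for that visit are in SAP 5.2.9, Table 6. The protocol interval is "Time of Dose + 7 days" and the analysis interval is "Time of Dose $+ 2$ to 21 days". Protocol 4.3.4 words the visit as "Patients will return to the study site within 7 days of study treatment (+2 days".

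On retesting, Protocol 8.1.5 asks that, where possible, "timely confirmation of the initial liver-related laboratory abnormalities should occur prior to the reporting of a potential DILI event". For other tests, Protocol 1.3.4 says only: "Clinicians should also monitor changes in hematology and other laboratory measures".

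**The concern.** A shift table is there to show who moved out of the normal range. A rule that chooses by calendar distance can drop the very value that shows the move. A visit within 7 days of dosing permits a first sample before day 7. A prompt recheck of an abnormal early sample will tend to fall nearer day 7, and it may find that the value has recovered. The subject is then tabulated as Normal. The same abnormality first seen on day 7 or later would be kept against any later-day repeat.

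What is at stake is the completeness of the safety tables. The SAP's exploratory objectives (1.2.3) include the frequency of laboratory abnormalities of clinical relevance. Appendix 1 marks the hematology, chemistry and transaminase shift tables as topline output. No efficacy result is touched.

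**Working it through.** The plan gives no figure to reproduce, so the check applies the rule by whole days after the dose.

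**Inputs.** Target day T = 7 and interval day 2 to day 21 (SAP Table 6); closest value is kept and ties go to the latest record (SAP 6.3). Let the first, abnormal sample fall on day d and one later repeat on day r.

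**Assumption.** A repeat inside day 2 to 21 belongs to the End of Treatment visit.

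**Condition.** The repeat replaces the first value when |r − 7| ≤ |d − 7|. For d < 7 this means any r from d + 1 to 14 − d. For d ≥ 7 a later day is always further from 7, so the first value stays.

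| First sample (day d) | Repeat days that replace it | Number | Last day (a tie) |
|---|---|---|---|
| 2 | 3 to 12 | 10 | 12 |
| 3 | 4 to 11 | 8 | 11 |
| 4 | 5 to 10 | 6 | 10 |
| 5 | 6 to 9 | 4 | 9 |
| 6 | 7 to 8 | 2 | 8 |
| 7 or later | none | 0 | – |

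In total 10 + 8 + 6 + 4 + 2 = 30 day pairs, 5 of them ties, out of 19 + 18 + … + 1 = 190 ordered pairs in the interval. If the first sample is held to day 9 (7 + 2, as in Protocol 4.3.4), it is 30 of 124. These are counts of day combinations, not probabilities; the documents do not say how samples or retests are distributed over days.

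**Illustration (invented values).** ALT is 4x ULN on day 4 and 0.9x ULN on day 9. The distances are |4 − 7| = 3 and |9 − 7| = 2, so the day 9 value is used. Table 14.4.6 shows Normal, while Table 14.4.7, which counts any post-randomization measurement, includes the subject above 3x ULN.

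**What else keeps the displaced value** (SAP 6.2, 6.3, 6.3.1 and Appendix 1; Protocol 8.2.2):

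| Displaced finding | Other planned output |
|---|---|
| AST/ALT above 3x ULN | Counted in Table 14.4.7; liver listing; maximum ALT on the eDISH plot |
| Bilirubin above 1x ULN; ALP above 1.5x ULN | Counted in Table 14.4.7 |
| AST/ALT elevation with an on-study AE of nausea, vomiting, anorexia, abdominal pain or fatigue | Counted in Table 14.4.7 |
| AST/ALT between 1x and 3x ULN without such an AE | No other laboratory count; maximum ALT appears as a point on the eDISH plot; listings |
| Hematology and non-hepatic chemistry such as CPK or creatinine | No other laboratory count; listings |
| Any result judged clinically significant or needing corrective therapy | Captured as an AE and so in the AE tables |

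**If the assumption fails.** If a retest is treated as unscheduled and outside the visit, it cannot replace the first value and the 30 pairs become 0. In that case an abnormality seen only at an unscheduled sample is missing from the by-visit shift tables instead. The SAP does not say which reading applies.

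**The case against.** The strongest objection is that little of importance is lost. Everything in the first three rows of the coverage table is counted from all post-randomization values, and anything clinically significant becomes an AE whatever the retest shows. A reader might infer that a displaced abnormality survives only in a listing, or that a liver signal could vanish. The documents do not support either. This part of the objection stands.

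Second, the link to the visit is assumed. The rule speaks of the same visit, and Table 6 is headed for efficacy analysis. That is fair. Still, it is the only source of an End of Treatment target, and a closest-to-target rule has work to do only if values from different dates can share a visit.

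Third, a reader might infer that the rule is biased towards a clean profile. The rule ignores the result, applies equally to both arms, and can also replace an early normal value with a later abnormal one. The only retest request is for liver values before a potential DILI report, and those are protected already. No retest is required for hematology or other chemistry, and no figure shows how often samples precede day 7. A lean towards hiding transient abnormalities is plausible where retests follow abnormal results, but its size cannot be stated.

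Fourth, Tables 14.4.6 and 14.4.7 answer different questions, by-visit shift and any occurrence, so unequal counts are not an error. That is true, but both are topline and nothing in the SAP warns the reader.

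Finally, Protocol 9.1 lists laboratory abnormalities among the tabulations of unique subjects with an event. Appendix 1 contains no such general table, so this does not close the gap.

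**Conclusion.** The point holds in a limited form. On the assumption that repeats within day 2 to 21 belong to End of Treatment, an abnormal first sample on days 2 to 6 is displaced from the shift tables by a repeat at least as close to day 7. A first sample on day 7 or later is not displaced by a later-day repeat.

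The consequence is incomplete counts of abnormal subjects for hematology, non-hepatic chemistry and asymptomatic AST/ALT elevations between 1x and 3x ULN, plus a possible unexplained difference between Tables 14.4.6 and 14.4.7. The main hepatic signal, the AE tables and all efficacy conclusions are unaffected. The number of subjects involved cannot be estimated from the documents. This is a modest weakness that is cheap to remove, not evidence that the safety profile is misrepresented.

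**What to change.** In SAP 6.3, state that the shift tables (14.4.3 to 14.4.6) use each subject's worst on-study value in each direction, highest for the high shift and lowest for the low shift. Include repeat and unscheduled samples within the on-study window that 6.3 already defines (after the dose, up to 30 days). Under this rule 0 of the 190 day pairs lose the abnormal first value, and the question of which visit a retest belongs to no longer matters for these tables. It also matches the plan's use of maxima for eDISH and of greatest intensity for AEs.

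The closest-to-target rule can stay for the continuous change-from-baseline tables (14.4.1 and 14.4.2). Replacing it there, for instance with the first post-dose value, would be a preference: that choice could keep a spurious first sample and discard a later real abnormality.

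The cost is a wording change, retitling of the affected shift tables, which are now labelled by visit, and minor programming. No new data are needed. Abnormality counts will be slightly higher in both arms.

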6.3.1 Liver Toxicity Evaluation

Potential drug induced liver injury are those events meeting Hy's Law, defined as:

- 1. Aminotransferases (AT) ALT or AST elevation > 3 times the upper limit of normal (ULN);
- 2. Total bilirubin (TBL) > 2 times ULN, without initial findings of cholestasis (elevated serum alkaline phosphatase); and
- 3. No other immediately apparent possible causes of AT elevation and hyperbilirubinemia, included but not limited to: viral hepatitis, pre-existing chronic or acute liver disease, or the administration of other drug(s) known to be hepatotoxic.

Any potential drug-induced liver injuries (DILIs), meeting the above defined criteria, will be reported as SAEs and tabulated by treatment group. A listing will be prepared that shows the AT and TBL values for all subjects that experience either AT > 3 times the upper limit of normal or TBL > 2 times the upper limit of normal at any time during the study.

Additionally, a table will be created that summarizes the incidence (as the number of subjects experiencing the given measurement post-randomization) of the following:

- >3x, >5x, >10x, and >20x ULN elevations of AST, ALT, and either ALT or AST
- Any elevations of bilirubin >1x ULN and >2x ULN
- Any elevations of ALP > 1.5x ULN
- Elevation of AST or ALT (>3x ULN) accompanied by elevated bilirubin (>1.5x ULN and >2x ULN)
- Elevation of AST or ALT along with an on-study AE of nausea, vomiting, anorexia, abdominal pain, or fatigue

An evaluation of Drug-Induced Serious Hepatotoxicity (eDISH) plot will be created by plotting the maximum total bilirubin against maximum ALT and presenting these data points by treatment group. The maximum values for each subject during the study will be identified as the maximum values that occur post-baseline, but not necessarily concurrently. Maximum total bilirubin (presented as xULN) will be plotted on a log scale on the y-axis and maximum ALT (presented as xULN) will be plotted on a log scale on the x-axis. A horizontal reference line will be placed at 2x ULN for maximum total bilirubin and a vertical reference line will be placed at 3x ULN for maximum ALT. The lower left quadrant will be labeled "Normal Range". The upper left quadrant will be labeled "Hyperbilirubinemia". The lower right quadrant will be labeled "Possible Hy's Law Range".

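### The eDISH plot in SAP 6.3.1 puts the 'Possible Hy's Law' label on the quadrant that fails the bilirubin criterion and gives no label to the quadrant where both thresholds are exceeded

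*SAP*

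**What the plan says.** SAP 6.3.1 (Liver Toxicity Evaluation) first defines potential drug-induced liver injury as events meeting Hy's Law. The first two of its three conditions are laboratory thresholds:

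- "Aminotransferases (AT) ALT or AST elevation > 3 times the upper limit of normal (ULN"), and
- "Total bilirubin (TBL) > 2 times ULN, without initial findings of cholestasis (elevated serum alkaline phosphatase); and"

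The third condition is that no other cause is immediately apparent. Protocol 8.1.5 gives the same definition.

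The same SAP section then specifies the eDISH plot:

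- Vertical axis: "Maximum total bilirubin (presented as xULN) will be plotted on a log scale on the y-axis".
- Horizontal axis: "maximum ALT (presented as xULN) will be plotted on a log scale on the x-axis".
- Bilirubin line: "A horizontal reference line will be placed at 2x ULN for maximum total bilirubin". A vertical line goes at 3x ULN for ALT.
- Each subject is plotted at the post-baseline maxima, which need not come from the same sample.
- Labels: lower left is the normal range, upper left is hyperbilirubinemia, and for the third: "The lower right quadrant will be labeled 'Possible Hy's Law Range". No label is given for the upper right.

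SAP Appendix 1 lists the plot as Figure 14.3.1, in treated subjects, and marks it as a topline output.

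**The concern.** An eDISH plot is read by quadrant: a reader looks for points in the quadrant marked as possible Hy's Law and treats the rest as lower concern. A label on the wrong quadrant misleads in two directions. Subjects with raised ALT and bilirubin within 2x ULN would appear as possible Hy's Law cases. Subjects above both thresholds would sit in an area that carries no marking.

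This matters more here than in most trials. Protocol 1.3.4 names potential change in liver function tests as the primary identified adverse event of interest, and Protocol 9.4.3 promises graphical as well as tabular liver displays. Figure 14.3.1 is the only safety figure in the SAP's figure lists. It would be released with the topline liver toxicity table (14.4.7) and the topline potential liver injury listings (16.2.10.8.1 and 16.2.10.8.2), and as labelled it could visibly disagree with them.

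**Working it through.** The plan gives no figure to reproduce, so the check is one of logic: compare each quadrant with the section's own two laboratory thresholds.

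**Inputs (all SAP 6.3.1).** x = maximum post-baseline ALT in multiples of ULN, cut at 3. y = maximum post-baseline total bilirubin in multiples of ULN, cut at 2. Threshold test: aminotransferase > 3 and bilirubin > 2.

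**Quadrant by quadrant, for the plotted ALT and bilirubin.**

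| Quadrant | ALT | Bilirubin | Both thresholds exceeded? | Label in the SAP |
|---|---|---|---|---|
| Lower left | ≤ 3x | ≤ 2x | No | Normal range |
| Upper left | ≤ 3x | > 2x | No | Hyperbilirubinemia |
| Lower right | > 3x | ≤ 2x | No (bilirubin fails) | Possible Hy's Law |
| Upper right | > 3x | > 2x | Yes | None given |

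**Example subjects (illustrative values, in multiples of ULN).**

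- ALT 5, bilirubin 3: 5 > 3 and 3 > 2, so both thresholds are exceeded. The point falls in the upper right, which has no label.
- ALT 5, bilirubin 1: 5 > 3, but 1 is not > 2. The point falls in the lower right, labelled as possible Hy's Law.
- ALT 1, bilirubin 3: 1 is not > 3. The point falls in the upper left, labelled hyperbilirubinemia, which is correct.

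**Does using non-concurrent maxima rescue the label?** No. If a subject's maximum post-baseline bilirubin is at or below 2x ULN, no single post-baseline bilirubin exceeded 2x ULN. The lower right quadrant therefore cannot contain a post-baseline case that meets the definition, whatever the timing. In the upper right quadrant the two maxima may come from different samples, and cholestasis and other causes are not assessed. A point there is a candidate and not a confirmed case, which is what the word 'possible' in the label conveys.

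**Effect of moving the label.** With the label on the upper right, the first example falls under it. The second falls in the lower right, which then needs a label of its own.

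**The case against.** **The text may be damaged.** Three labels are given for four quadrants. If the PDF reading or the drafting lost one clause (a lower right label followed by the opening of a sentence on the upper right), the result would be exactly the sentence that stands. The documents cannot exclude this. However, the sentence is complete and grammatical, with no gap or redaction mark, and a drafting slip would still need correcting. What stands is that the source PDF should be checked first.

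**No case is lost.** A reader might infer that true Hy's Law cases could be missed or miscounted. The documents do not support that. The same section has potential liver injury events, defined on ALT or AST, reported as serious adverse events and tabulated by treatment group. It plans a table of AST or ALT above 3x ULN accompanied by bilirubin above 1.5x and above 2x ULN. It also plans a listing of aminotransferase and bilirubin values for every subject with aminotransferase above 3x or bilirubin above 2x ULN. This objection stands in full and limits the point to the figure.

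**Few points may be affected.** Each subject takes one dose, scheduled post-dose laboratory testing is at the End of Treatment Visit only (Protocol Table 1), and Protocol 5.3 excludes aminotransferases or bilirubin above 1x ULN at entry, with one repeat allowed for borderline values. This is plausible, but the documents give no expected number, and a small number of points does not make the label right.

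**The ALT-only axis.** A reader might also infer that using ALT alone is a second error, because the definition in Protocol 8.1.5 reads "Aminotransferases (AT) (ALT or AST) elevation > 3 times the upper limit of normal (ULN"). A subject with ALT 2x, AST 5x and bilirubin 3x ULN would appear under hyperbilirubinemia. But the SAP declares the axis openly ("plotting the maximum total bilirubin against maximum ALT"), that subject is plotted correctly for the declared axes, and the label is a true description. The figure is a screening display and does not claim to apply the full definition. This is a display choice that could be improved, not a mistake.

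**Conclusion.** The labelling error holds on the text as read. SAP 6.3.1 attaches the possible Hy's Law label to a quadrant that cannot satisfy its own bilirubin criterion and names no label for the only quadrant in which both plotted thresholds are exceeded.

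Its size is limited: one topline safety figure, and within it the labels of two quadrants. No point moves, and no safety count, serious adverse event rule, analysis population or efficacy test is affected. How many subjects would be shown under the wrong label cannot be derived from the documents.

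The conclusion assumes that the extracted text matches the source PDF. If the PDF contains a separate lower right label and puts the Hy's Law label on the upper right, the point falls away.

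**What to change.** 1. Check the source PDF of SAP 6.3.1 for a dropped phrase.
2. If the text stands, assign the possible Hy's Law label to the upper right quadrant and give the lower right its own label for isolated ALT elevation. Carry the same labels into the program for Figure 14.3.1.
3. Optionally, add an AST panel, or plot the larger of maximum ALT and maximum AST (each as a multiple of ULN) on the x-axis, so that the figure matches the ALT-or-AST definition. The illustrative subject with ALT 2x, AST 5x and bilirubin 3x ULN would then fall in the labelled quadrant. If the combined axis is used, the lower right label should refer to aminotransferase and not to ALT alone.

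The cost is a few words of SAP text and minor figure code. No new data are needed, and nothing changes for subjects or sites.
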